Primary	To compare the long-term effect of a blended care approach (interactive learning e-tool and face-to-face contacts with general practitioner) versus usual care on the discontinuation of (z-)BZD	Proportion of patients that discontinued (z-)BZD use at 12 months assessed by toxicological screening
Secondary	To compare the short-term effect of a blended care approach (interactive learning e-tool and face-to-face contacts with GP) versus usual care on the discontinuation of (z-)BZD	Proportion of patients that discontinued (z-)BZD use at 6 months assessed by toxicological screening
	To compare the effect of a blended care approach (interactive learning e-tool and face-to-face contacts with GP) versus usual care on the quality of life	EQ5D-3L assessed at week 6, 12, 26 and 52

	To compare the effect of a blended care approach (interactive learning e-tool and face-to-face contacts with GP) versus usual care on self-reported discontinuation of (z-)BZD use	Proportion of patients with self-reported discontinuation of (z-)BZD use assessed at week 6, 12, 26 and 52
	To compare the effect of a blended care approach (interactive learning e-tool and face-to-face contacts with GP) versus usual care on the number of defined daily doses (DDD) of benzodiazepines prescribed	The number of DDD of (z-)BZD prescribed in the preceding interval assessed at week 6,12,26 and 52

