3.5 Secondary endpoints

- The proportion of subjects with a negative benzodiazepine urine test assessed 6 months after initiation of the intervention.
- The proportion with a better score in quality of life from baseline to 6, 12, 26 and 52 weeks.

- The proportion of subjects that self-report to have ceased benzodiazepine use at 6, 12, 26 and 52 weeks.
- The number of DDD of benzodiazepines prescribed at 6, 12, 26 and 52 weeks from baseline.

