6 ELIGIBILITY CRITERIA

6.1 Inclusion criteria

Patients' eligibility for inclusion in the study will be based on the following criteria:

- Patients aged 18 and older capable of giving informed consent,
- Having his/her Global Medical File managed by one of the participating general practitioners
- Receiving prescriptions of (z-)BZDs from participating GP for use on a daily basis
- Reporting daily intake ($\geq 80\%$ of days) of (z-)BZDs in the last 6 months for a primary indication of sleeping problems

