7.6 Baseline data

At study entry, the following baseline data will be collected for each participating patient:

- Demographics, comorbidities and medication
- Toxicological screening of urine
- Self-reported use of (z-)BZD (drug name(s), quantity)
- (z-)BZD prescriptions in last 6 months (drug name(s), quantity)
- Audit-C
- EQ5D-3L
- Benzodiazepine Dependence Self-Report Questionnaire
- Insomnia Severity Index
- HLS-EU-Q16

Except for the toxicological screening for which the procedure is explained in 7.7, data will be collected either by completion of the eCRF or via questionnaires sent to the patient.

The invitation to complete the first questionnaire will be sent after signature of the Informed Consent Form (ICF) and registration of the patient in the online platform Slaapzorgeloos/Dormir Sereinement. This first (baseline) questionnaire should thus be completed before the baseline visit takes place. By doing so, we would like to prevent that the patients' answers are influenced by the outcome of the randomisation (see section 7.3.1 *method of implementing the allocation sequence*).

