10.3.3 Secondary outcome analysis

The proportion of subjects with a negative benzodiazepine urine test assessed 6 months after initiation of the intervention will be analyzed in the same way as the primary endpoint.

All other secondary endpoints are binary variables, measured longitudinally. Analysis will be performed using multilevel logistic regression analysis, including random intercepts for patient and for general practitioner. A random slope for time will be modelled if beneficial for model fit. The fixed effects model will include intervention group, time and the group by time interaction. In case of a significant group by time interaction, the group effect will be reported separately for each time point. In case of a non-significant group by time interaction, a group main effect will be reported. The group effects will be presented as odds ratios with 95% confidence intervals.

The EQ-5D-3L data will be summarized based on the principles of a Pareto improvement in Welfare Economics - the Pareto Classification of Health Change (PCHC) (Devlin 2010). According to this principle an EQ-5D-3L health state is deemed to be 'better' than another if it is better on at least one dimension, and is no worse in any other dimension. And an EQ-5D-3L health state is deemed to be 'worse' than another if it is worse in at least one dimension, and is no better in any other dimension. Using that principle to compare a patient's EQ-5D-3L health states between any 2 time periods, there are only 4 possibilities:

- Their health state is better
- Their health state is worse
- Their health state is exactly the same
- The changes in health are 'mixed': better on one dimension, but worse on another.

The EQ-5D-3L scores will be analyzed as (1) better versus other, and (2) worse versus other.

No correction for multiplicity is planned for the secondary analyses, as the study is not powered for these analyses, and hence, its results will be considered as hypothesis generating.

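### The longitudinal models for EQ-5D-3L and DDD omit baseline values that are collected; separately, patients with no problems at baseline can never count as better, and DDD has no suitable model

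*Combined protocol and SAP*

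**What the plan says.** Section 10.3.3 analyses the 6-month urine test like the primary endpoint and says of the rest: "All other secondary endpoints are binary variables, measured longitudinally". These are EQ-5D-3L, self-reported discontinuation and DDD prescribed. The method is multilevel logistic regression with random intercepts for patient and GP, and a random slope for time if it improves fit. The fixed part is: "The fixed effects model will include intervention group, time and the group by time interaction". The section names no baseline covariate and does not say whether time has a baseline level.

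For EQ-5D-3L, section 3.5 gives the endpoint as "The proportion with a better score in quality of life from baseline to 6, 12, 26 and 52 weeks". Section 10.3.3 applies the Pareto Classification of Health Change, under which one state beats another if it is "better on at least one dimension, and is no worse in any other dimension". It continues: "The EQ-5D-3L scores will be analyzed as (1) better versus other, and (2) worse versus other".

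For DDD, the Trial Summary gives "The number of DDD of (z-)BZD prescribed in the preceding interval assessed at week 6,12,26 and 52".

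At baseline, 7.6 collects EQ-5D-3L and "z-)BZD prescriptions in last 6 months (drug name(s), quantity". Baseline dose in DDD appears in the descriptive list in 10.3.1 and as a subgroup factor for the primary outcome in 10.3.2, but in no secondary model. EQ-5D-3L is absent from the 10.3.1 list.

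Section 10.3.3 also says that the study is not powered for the secondary analyses and that their results are hypothesis generating.

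**The concern.** There are three linked gaps.

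- **No baseline term.** The starting state affects the chance of being classed better or worse, and prior prescribing can be expected to predict later prescribing. Both are collected and neither is used as a covariate. The cost is precision, and any chance difference between arms at baseline goes straight into the estimate.
- **A ceiling in one EQ-5D contrast.** A patient with no problem on any dimension at baseline is fixed as *other* at every visit in *better versus other*. The result therefore mixes the intervention's effect with the share of patients who could improve at all. With EQ-5D-3L missing from the 10.3.1 list, a difference in that share would be neither adjusted for nor shown.
- **No workable DDD model.** A logistic model does not fit a number of DDD. A suitable model has to be written before a baseline term can be added to it.

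At stake is how clearly two secondary endpoints can be read.

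**Working it through.** **Inputs from the plan.** Section 10.1 gives 594 patients under individual randomisation, ICC 0.11, 10 patients per cluster and 10% loss. The design effect is 1 + 0.11 × 9 = 1.99, and 594 × 1.99 = 1182, or 591 per arm, which reproduces the stated total. The plan gives no figure for any secondary endpoint, no baseline EQ-5D distribution and no baseline-to-follow-up correlation. Everything below therefore rests on assumed ranges.

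**1. The ceiling.** EQ-5D-3L has 3^5 = 243 states. Enumerating all of them under the 10.3.3 rule, 0 are better than full health (level 1 on all five dimensions). This follows from the classification and does not depend on the model's covariates.

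**2. Effect of the ceiling share.** Let f be the share in full health at baseline. Assume 30% v 40% *better* among the others, so the all-patient proportions are 0.30(1 − f) and 0.40(1 − f). The information ratio is the squared z statistic with full-health patients set aside, divided by that with everyone. Power uses 1182 × 0.90 / 2 / 1.99 = 267 effective patients per arm, assuming that the ICC of 0.11 carries over.

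| f | Proportions | Odds ratio | Information ratio | Power, all | Power, restricted |
|---|---|---|---|---|---|
| 0 | 0.30 v 0.40 | 1.56 | 1.00 | 0.68 | 0.68 |
| 0.2 | 0.24 v 0.32 | 1.49 | 1.11 | 0.54 | 0.58 |
| 0.4 | 0.18 v 0.24 | 1.44 | 1.22 | 0.40 | 0.47 |

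These are marginal, single-visit odds ratios. The planned model reports odds ratios conditional on patient and GP intercepts, so the table shows direction and rough size only.

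**3. Chance imbalance, no true effect.** Take 27% v 33% at the ceiling and 30% *better* among the others in both arms:

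- 0.73 × 0.30 = 0.219 and 0.67 × 0.30 = 0.201
- odds ratio = (0.219/0.781) / (0.201/0.799) = 1.11

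The standard error of such a difference at 30% is √(2 × 0.3 × 0.7/591) = 2.7 points, or 2.7 × √1.99 = 3.8 points with the full design effect. Six points is thus 2.25 or 1.6 standard errors: possible, not typical. The log odds ratio of 0.109 is 0.76 of its own standard error without clustering and 0.54 with it.

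**4. DDD.** In a linear model, adjusting for a baseline value with correlation r multiplies residual variance by 1 − r²:

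- r = 0.5: 1 − 0.25 = 0.75, or 25% less
- r = 0.7: 1 − 0.49 = 0.51, or 49% less
- over a wider range, r = 0.3 gives 9% less and r = 0.8 gives 64% less

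The outcome intervals ending at weeks 6, 12, 26 and 52 last 6, 6, 14 and 26 weeks, and the baseline window is 6 months. Raw totals are not comparable across them; DDD per day is.

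**5. Self-reported discontinuation.** Section 6.1 requires reported intake on at least 80% "of days) of (z-)BZDs in the last 6 months for a primary indication of sleeping problems". Every patient is a daily user at entry, so this outcome has no baseline variation to adjust for.

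**The case against.** Several objections have force.

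- **A reader might infer that the missing covariate causes the ceiling.** It does not. The ceiling comes from the classification, and a patient in full health at baseline remains *other* whatever is adjusted for. Nor is baseline wholly unused, since the EQ-5D outcome is itself a comparison with baseline.
- **Dilution is partly a choice of estimand.** Section 3.5 defines the endpoint over all patients. Setting aside those at the ceiling answers a different question, and *worse versus other* already counts full-health patients who decline. This rules out replacing the endpoint. It does not rule out a supplementary analysis.
- **A reader might infer bias.** Under randomisation the imbalance is a matter of chance, and the confidence interval allows for it. What is lost is precision.
- **A reader might apply the 25-49% to the planned analysis.** It is a linear-model result and has no meaning for the logistic model now specified.
- **These endpoints are hypothesis generating.** That limits the severity. It is no reason to leave collected baseline data out of the models.

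If time had a baseline level, DDD could use prior prescribing as a first measurement, but the plan does not say so. The EQ-5D contrasts have no baseline value of their own.

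**Conclusion.** The point holds for EQ-5D-3L and DDD and is minor. Section 10.3.3 names no baseline covariate although the values are collected, which costs precision and leaves chance imbalance unadjusted. As a separate matter, *better versus other* depends on the ceiling share in each arm: an odds ratio of about 1.11 with no effect at 27% v 33%, given an assumed 30% *better* among the rest. The DDD endpoint lacks a model that suits it. The possible gain of 25-49% of residual variance assumes correlations of 0.5-0.7 and arises only once a linear model replaces the logistic one.

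The documents do not support extending the point to self-reported discontinuation, to the sample size or to the primary analysis.

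**What to change.** In 10.3.3:

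- **EQ-5D-3L.** Add the baseline state, for example the index value, as a covariate in both EQ-5D models, and name the value set if the index is used. A simple full-health indicator would not work in *better versus other*, because no patient in that category can have the event.
- **Ceiling.** Keep the all-patient endpoint of 3.5. Report *better versus other* in patients with at least one baseline problem as a supplementary analysis only. Adding baseline EQ-5D-3L to the 10.3.1 list would show the share at the ceiling by arm.
- **DDD.** Remove DDD from the binary endpoints. Analyse DDD per day in each interval with a continuous or count mixed model, with baseline DDD per day over the prior 6 months as a covariate.

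The cost is SAP wording, one replaced model and one supplementary analysis. No new data are needed. The supplementary result applies only to patients who can improve and should be labelled so.

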3.1.3 Self-reported use of benzodiazepines

The third secondary objective is to compare the effect of blended care combining an interactive educational e-tool with face-to-face clinical consultations versus usual in terms of self-reported discontinuation of (z-)BZD use in a population of adult primary care patients chronically using benzodiazepines for a primary indication of sleeping disorders.

Null hypothesis: blended care is not superior to usual care in terms self-reported discontinuation of benzodiazepine use.

Alternative hypothesis: blended care increases self-reported discontinuation compared to usual care.

PICOT

Population:	Patients receiving prescriptions for (z-)BZD on a daily basis in the last 6 months for a primary indication of sleeping problems aged 18 and older.
Intervention	Blended care combining an interactive educational e-tool with face-to-face clinical consultations with the GP.
Comparator	Care as usual for chronic (z-)BZD use left at the discretion of the GP. This may include a minimal intervention (discontinuation letter or discontinuation advice) or a more extended intervention, in combination with (z-)BZD tapering.
Outcome	Self-reported discontinuation of (z-)BZD.
Time	The outcome will be assessed at week 6, 12, 26 and 52.

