3.1.4 Prescriptions for benzodiazepines

The fourth secondary objective is to compare the effect of blended care combining an interactive educational e-tool with face-to-face clinical consultations versus usual care on the number of DDD of (z-)BZD prescribed at 6, 12, 26 and 52 weeks from baseline in a population of adult primary care patients chronically using benzodiazepines for a primary indication of sleeping disorders.

Null hypothesis: blended care is not superior to usual care in terms the number of DDD of benzodiazepines prescribed at 6, 12, 26 and 52 weeks from baseline.

Alternative hypothesis: blended care will decrease the number of DDD of (z-)BZD prescribed at 6, 12, 26 and 52 weeks from baseline compared to usual care.

PICOT

Population: Patients receiving prescriptions for (z-)BZD on a daily basis in the last 6 months for a primary indication of sleeping problems aged 18 and older.

Intervention Blended care combining an interactive educational e-tool with face-to-face clinical consultations with the GP.

Comparator Care as usual for chronic (z-)BZD use left at the discretion of the GP. This may include a minimal intervention (discontinuation letter or discontinuation advice) or a more extended intervention, in combination with (z-)BZD tapering.

Outcome The number of DDD of (z-)BZD prescribed.

Time The outcome will be assessed 6, 12, 26 and 52 weeks after initiation of the intervention.

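### Minor and cheap to improve: for the longitudinal secondary endpoints the model-based odds ratio at each visit is reported only if an unpowered group-by-time test is significant

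*Combined protocol and SAP*

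**What the plan says.** Section 10.3.3 analyses the 6-month urine test "will be analyzed in the same way as the primary endpoint", that is, with a single-time logistic model. It treats all remaining secondary endpoints as binary and longitudinal. They get a multilevel logistic model with random intercepts for patient and GP, and with group, time and group by time as fixed effects. A significant interaction leads to a group effect at each time point. If it is not significant, "In case of a non-significant group by time interaction, a group main effect will be reported". The section adds: "A random slope for time will be modelled if beneficial for model fit". It states neither the coding of time in the fixed part nor a significance level for the interaction test.

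The endpoints themselves are tied to visits. The Trial Summary lists "EQ5D-3L assessed at week 6, 12, 26 and 52". Section 3.1.3 says of self-reported discontinuation: "The outcome will be assessed at week 6, 12, 26 and 52". Section 3.5 defines the endpoint as "The proportion of subjects that self-report to have ceased benzodiazepine use at 6, 12, 26 and 52 weeks". Section 3.1.4 puts the visits into the hypothesis itself: "blended care will decrease the number of DDD of (z-)BZD prescribed at 6, 12, 26 and 52 weeks from baseline".

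Section 10.3.3 plans no multiplicity correction, "as the study is not powered for these analyses", and calls the results hypothesis generating.

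**The concern.** The rule uses a significance test to decide which estimate the reader sees. Failing to reject a constant effect is weak evidence for one, and weaker still in analyses the plan itself calls unpowered. If the odds ratio does change over time and the test misses it, the report carries one model-based figure. That figure can be too high at some visits and too low at others, and the visit-specific estimates with intervals that respect clustering by GP are not shown.

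The deciding test is also not fixed in advance. Categorical time gives a 3-df test over four visits and linear time a 1-df test. On the same data these can send the report down different branches.

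What is at stake is how informative the secondary results are, chiefly at weeks 6 and 12 and for EQ-5D at every visit, where no other model-based estimate is planned.

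**Working it through.** **The plan's own figure.** Section 10.1 can be reproduced. Comparing 15% with 25% at two-sided 0.05 and 80% power gives 250 per arm. The continuity correction gives (250/4) × (1 + √(1 + 4/(250 × 0.10)))² = 269.6, so 270. Then 270 × 1.10 = 297 per arm, or 594. The design effect is 1 + 0.11 × 9 = 1.99; 594 × 1.99 = 1182, hence 119 GPs. This point disputes none of these figures.

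**Text check.** The endpoint definitions name four visits, and the reporting rule may return one number for all four. No other section promises the visit-specific odds ratios regardless of the test.

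**Illustration, self-reported cessation only.** From the documents: 120 GPs, 10 patients each less 10% loss (9 analysed), ICC 0.11, and 15% v 25% at week 52, which is borrowed from the urine endpoint. Assumed: every other visit rate, the ICC placed on the latent scale, a patient variance of 3 or 6, and an interaction level of 0.05. The test is a 3-df Wald test on the population-averaged log odds ratios with GP-robust variance. Control rates are 3/6/12/15% at weeks 6/12/26/52, except in the waning pattern (5/10/14/15%).

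| Pattern | Blended care, % | Odds ratios | Power, 3 df | Missed | Median single OR when missed |
|---|---|---|---|---|---|
| Delayed | 3/6/15/25 | 1.00/1.00/1.29/1.89 | 66–70% | 30–34% | about 1.5 |
| Growing | 3/7/17/25 | 1.00/1.18/1.50/1.89 | 45–51% | 49–55% | about 1.6 |
| Gradual | 3.5/8/18/25 | 1.17/1.36/1.61/1.89 | 26–28% | 72–74% | about 1.65 |
| Waning | 10/19/23/20 | 2.11/2.11/1.83/1.42 | 40–49% | 51–60% | about 1.8 |

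Example of an odds ratio: (0.25/0.75)/(0.15/0.85) = 1.89. Repeat runs agree within a few points. With a constant odds ratio of 1.6 the test rejects in about 5%, as it should.

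**A second approximation.** This takes a per-arm effective sample of 591 × 0.9/1.99 = 267, slightly different assumed rates and within-patient correlation 0.3–0.7. Power is 30–51% for a growing effect and 27–56% for a waning one. For an effect confined to week 52 it is 61–93%, so a sharp late effect would usually be detected. Without the design effect the growing and waning figures become 55–83% and 51–87%.

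**Coding of time.** With 1-df linear time, power in the four patterns is 74–85%, 62–71%, 38–47% and 44–64%, higher than with 3 df. For an assumed rise and relapse (blended care 3/10/24/20%; odds ratios 1.00/1.74/2.32/1.42) it is 72–78% with 3 df but only 5–11% with 1 df. The unstated coding can therefore decide the branch.

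**The case against.** Testing the interaction first and then reporting is a common, pre-specified convention. The hypotheses in 3.1.2 and 3.1.3 are overall ones, with the weeks given as assessment times, and a main effect answers them. Only 3.1.4 writes the visits into the hypothesis. Its outcome is a number of doses, to which no odds ratio applies without a cut-off; that is a separate matter. All this stands and limits the point to an improvement.

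A reader might infer that the documents themselves predict a changing effect, because tapering takes weeks and section 3.3 describes a relapsing disorder. They do not support this. The Trial Summary gives the same typical taper for both arms. A shared taper explains low quit rates early on, which the time main effect absorbs, and it implies nothing about the odds ratio. Relapse can occur in either arm, and section 3.3 uses it to justify the 52-week time point.

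The numbers also have limits. The visit rates were chosen to vary over time, and the planned mixed model, with its conditional odds ratios, was not fitted. A recovered week-6 estimate may say little: at 3% there are about 540 × 0.03 = 16 events per arm. An odds ratio of 1.00 then has a 95% interval of roughly 0.5–2.0 before clustering.

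Finally, nothing bars tabulating proportions per arm and visit. That helps, but crude intervals built from them ignore clustering. With 9 patients per GP and an observed-scale ICC of 0.11, the design effect is 1 + 8 × 0.11 = 1.88, the standard error is too small by √1.88 = 1.37, and a nominal 95% interval covers about 85%.

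**Conclusion.** The point holds as a minor one. The wording of 10.3.3 makes visit-specific model estimates depend on a test that the plan does not power and does not fully define. A non-significant result cannot justify withholding them. This conclusion rests on the text and needs no simulated value.

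The miss rate of roughly 30–74% belongs to four assumed patterns, a 3-df test and a marginal model. It shows that the rule can fail, not how often it will fail in this trial.

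It would be wrong to infer that the trial's conclusions on discontinuation are at risk. The 6- and 12-month urine endpoints have their own single-time models outside this rule, the affected analyses are hypothesis generating, and no confirmatory conclusion changes.

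**What to change.** Replace the two-branch rule in 10.3.3 with:

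> Time is a categorical fixed factor. For each binary longitudinal secondary endpoint, the group odds ratio with 95% CI is reported at weeks 6, 12, 26 and 52 from the model including group by time, whatever the interaction result. The interaction p-value is descriptive, and the overall group odds ratio, from the same model without the interaction, is reported alongside. Any random slope uses time as a continuous variable.

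This takes a few sentences, with no new data and no change to sample size or alpha. There are two costs. Visit-specific intervals are wider than the overall one: in the simulation about 2 times at week 6 (range 1.6–2.3) and close to 1 at week 52 (1.0–1.2). There are also more uncorrected estimates: three outcomes (self-reported cessation, EQ-5D better, EQ-5D worse) × 4 visits = 12 odds ratios besides the 3 overall ones.
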